5 STUDY ENDPOINTS

5.1 PRIMARY ENDPOINTS

The primary study endpoints are percentage of limbs with vein occlusion in the treated vein and the absence of reflux in the treated vein, as determined by Duplex Ultrasound Scan (DUS).

Primary endpoint analysis will be accomplished by measuring the treated vein recanalization and reflux rates at 3 days (+/- 2 days), 3-months (+/- 2 weeks), 6 months (+/- 3 weeks) and 12 months (+/- 4 weeks) post-procedure. Recanalization will be determined by DUS and clinical assessment during follow-up. A twelve-month follow-up is sufficient to assess a stable occlusion in the treated vein, as it is the typical final follow-up time frame for varicose vein treatment when assessing technical and symptomatic recurrence.

Specific primary endpoint measurements will be:

 Vein Occlusion Rate – percentage of limbs with occlusion of the treated vein: Occlusion is defined as the absence of any flow from 3 cm inferior to the Saphenofemoral Junction (SFJ) along the entire length of the treated vein as documented on the post-procedure and follow-up DUS. The 3 cm limit was selected

Document Title: EU Post Market Clinical Follow-Up Study of the Venclose System for Saphenous Vein Incompetence

to represent the occlusion status of the proximal Great Saphenous Vein (GSV) and to allow precise evaluation with a typical 4 cm linear ultrasound probe. In line with the equivalent ClosureFast device clinical studies^{2,3} flow in the stump of the GSV up to 3 cm below the SFJ is considered normal and does not constitute a failure.

2) Reflux-Free Rate – percentage of limbs without reflux in the treated vein: Reflux is measured by Duplex Ultrasound imaging along the entire treated vein segment(s). Reflux is defined as reversal flow >0.5 seconds with subject standing or in reverse Trendelenburg position of at least 15° after distal augmentation.

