Participant	Twelve months post-procedure
Duration	
Study Site(s)	One study site located in Germany
Sample Size	Up to 25 subjects treated with the Venclose System
	Baseline Visit Treatment Visit Follow-Un Visits (3-day 3-month 6-
Study Visits	month and 1 year post procedure)
	month, and T year post procedure)
	1. Vein Occlusion Rate (percentage of limbs with occlusion of the treated
	vein) at 3-day, 3-month, 6-month, and 12-month Follow-up Visits.
Primary	
Endpoints	2. Reflux-free Rate (percentage of limbs without reflux, as determined by
	Duplex Ultrasound Scan) at 3-day, 3-month, 6-month, and 12-month
	Follow-up Visits.
Secondary	Clinical signs and symptoms of lower limb venous disease at baseline 2
Endnointe	months 6 months and 12 months as measured by
Enupoints	monuis, o monuis, and 12 monuis as measured by:

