3 TECHNOLOGY SUMMARY

The Venclose[™] Radiofrequency (RF) System (Generator and Catheters) is intended for use in endovascular coagulation of blood vessels in patients with superficial vein reflux. The Venclose System uses resistive radiofrequency ablation via bipolar energy delivery to heat the wall of an incompetent vein with temperature-controlled RF energy to cause irreversible luminal occlusion, followed by fibrosis and ultimately resorption of the vein. The blood then naturally reroutes to healthy veins.

The technique involves percutaneous access and insertion of the endovenous sectional radiofrequency (EVSRFTM) catheter into the target vein under ultrasound guidance and relies on the use of local anesthesia and thermal energy, from a radiofrequency generator, applied to the target vein. After each treatment, the EVSRF catheter is withdrawn a single length of the heating coil and another treatment is performed, until the entire vessel has been treated. This sectional treatment involves thermal damage that is inflicted upon the venous endothelium and into the wall, resulting in contraction and ultimately destruction of the vessel.

Document Title: EU Post Market Clinical Follow-Up Study of the Venclose System for Saphenous Vein Incompetence

The procedure can be performed in an outpatient setting, without the need for general anesthesia, allowing for a walk-in/walk-out procedure with minimal postoperative recovery time.

The Venclose System consists of two (2) main components: 1) The EVSRF Ablation catheter (model VC-10A2.5-6F-60, 60cm or VC-10A2.5-6F-100, 100cm) with integrated cable connector which, using sectional ablation, treats the vein in 10 cm or 2.5 cm segments, and 2) the Venclose digiRF generator (model VC-RFG-1) which delivers RF energy to the EVRSF catheter.

The Venclose System is comprised of the following accessories:

- Power cord for generator for the geographical region that the generator is sold
- Optional foot pedal (model VC-FP-1)

The following supplies are necessary for the procedure, but are not provided with the Venclose System:

- Duplex or B-mode ultrasound console
- Supplies for sterile procedure
- Tilt table (recommended)
- 6F introducer sheath, with matching dilator, guidewire and percutaneous access needle (access kit/ introducer kit)
- Local or general anesthesia
- Post-operative compression as recommended by physician

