6.2 EXCLUSION CRITERIA

- 1. There is evidence of old or fresh thrombus in the subject's diseased vein segment to be treated, as determined by DUS within 2 weeks prior to the index procedure.
- 2. In the judgment of the treating investigator heat energy delivery to the subject would be contraindicated.
- 3. Subject is concurrently participating in another interventional clinical trial.
- 4. Subject is pregnant or plans to be pregnant or lactating at the time of the treatment procedure.
- 5. Subject has known or suspected allergies or contraindications to any general or local anesthetic agents and/or any antibiotic medication that cannot be adequately pre-treated.

7 PRE-SURGICAL ASSESSMENT (Baseline Study Visit)

Potential subjects will be examined by the Investigator or his/her designee and evaluated according to the inclusion/exclusion criteria for participation in this study. Demographics, medical history (including previous venous interventions, risk factors/co-morbidities, and

Document Title: EU Post Market Clinical Follow-Up Study of the Venclose System for Saphenous Vein Incompetence

concomitant conditions/medications), and a venous Duplex Ultrasound will be performed during pre-surgical assessment, and the results recorded on the *Baseline Case Report Form*.

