8 SURGICAL PROCEDURE

In accordance with routine clinical commercial practice, study investigators will receive in-service training by Venclose personnel or its representatives for the use of the Venclose System as well as product labeling and training materials, which include the Venclose digiRF User Manual (LB00003) (generator) and Venclose Catheter IFU (LB00002).

The surgical procedure with the Venclose System will be conducted in accordance with the EU approved Venclose Catheter IFU and the Venclose digiRF User Manual (generator). The typical training program for the commercial device includes information about supplies, patient preparation, vein access, skin marking and measurement, device preparation, insertion, placement and local anesthetic, energy delivery and post-surgery recovery. Training that is specific to the performance of the study includes documentation requirements and procedures for the timely transmission of data. Procedure details and adverse events assessment will be recorded on the *Treatment Visit Case Report Form and Adverse Event Case Report Form*.

The Venclose procedure will be performed on the GSV per standard of care. For the GSV, no other treatment modalities are allowed (i.e. no phlebectomy or sclerotherapy).

Adjunctive procedures for treatment of side branches (i.e. anterior accessory saphenous vein) may be performed per standard of care including phlebectomy and sclerotherapy.

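### Reflux is measured only over the treated segment(s), the treated vein is undefined and incomplete ablation has no scoring rule, so a limb with residual GSV reflux can count as reflux-free

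*Combined protocol and SAP*

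**What the plan says.** The reflux-free rate is worded in three ways.

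- **Synopsis, Primary Endpoints:** "Reflux-free Rate (percentage of limbs without reflux, as determined by" duplex ultrasound (DUS). This carries no restriction to a vein or segment.
- **Section 5.1, endpoint label:** "percentage of limbs without reflux in the treated vein".
- **Section 5.1, measurement sentence:** "Reflux is measured by Duplex Ultrasound imaging along the entire treated vein segment(s".

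Occlusion, also in Section 5.1, is the "absence of any flow from 3 cm inferior to the Saphenofemoral Junction (SFJ) along the entire length of the treated vein". Its upper end is a fixed anatomical point. Its lower end is wherever the treated vein ends. Flow in the stump above the 3 cm point is expressly not a failure.

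Other sections bear on the intended extent of treatment.

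- Section 3 describes section-by-section withdrawal of the catheter "until the entire vessel has been treated".
- Exclusion criterion 1 in Section 6.2 presupposes a segment identified before the procedure: "There is evidence of old or fresh thrombus in the subject's diseased vein segment to be treated".
- Section 8 says of the index treatment: "For the GSV, no other treatment modalities are allowed".
- Sections 10.1 and 10.2 have the follow-up scan assess the treated GSV, while Section 10.3 speaks of a treated GSV segment.

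No passage defines the treated vein, requires a target length to be recorded from the baseline DUS, defines technical success, or classifies a partial ablation.

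**The concern.** The study objective is to confirm performance in ablating incompetent GSVs. If the scored region is whatever was ablated, the outcome of the procedure determines the region over which the procedure is judged. A pullback that ends early, for example after a perforation or a device fault, leaves a shorter region to score. The limb stays in the denominator, and what was left open need not count against it.

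This error has only one direction. When the ablated part lies within the segment meant for treatment, every limb that succeeds over the whole segment also succeeds over the ablated part. The treated-segment rate therefore cannot be lower than the intended-segment rate. The two are equal only if no untreated part shows flow or reflux in a limb that otherwise succeeds.

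The differing wordings add a second problem. The same limb can be a success or a failure on a primary endpoint depending on which sentence the assessor follows, and that choice could be made after the scans have been read.

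**Working it through.** **Step 1. Classify a short procedure under each wording.** Suppose the ablated part is closed and reflux-free, and the untreated part of the intended GSV still has flow and reflux.

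| Untreated part | Reflux, Section 5.1 measurement sentence | Reflux, synopsis read literally | Occlusion, treated vein = length ablated | Occlusion, treated vein = GSV |
|---|---|---|---|---|
| Distal | Success | Failure | Success | Failure |
| Proximal, more than 3 cm below the SFJ | Success | Failure | Failure | Failure |

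The Section 5.1 reflux sentence passes the limb in both rows. Occlusion passes it in one cell only, because the 3 cm anchor brings residual proximal flow into the scored region. The distal row matters in practice. The catheter is withdrawn section by section, and the stump rule suggests that treatment begins near the SFJ. On that inference, an early stop leaves the distal part untreated.

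**Step 2. Size per limb.** The plan has no figure to reproduce: it gives no assumed rate, margin, alpha or power. The inputs are:

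- up to 25 treated subjects (synopsis; Section 6);
- bilateral limbs analysed separately in per-limb analyses (note in Section 7.3), so between 25 and 50 limbs if all 25 subjects are treated;
- k, the number of short limbs with residual flow or reflux, which is an assumption.

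Shift in the rate per limb = 1/n: 1/25 = 4 points; 1/50 = 2 points.

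Exact (Clopper-Pearson) 95% intervals, with every other limb a success:

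| Limbs n | k | Rate (n − k)/n | 95% CI |
|---|---|---|---|
| 25 | 0 | 100% | 86.3 to 100 |
| 25 | 1 | 96% | 79.6 to 99.9 |
| 25 | 2 | 92% | 74.0 to 99.0 |
| 25 | 3 | 88% | 68.8 to 97.5 |
| 50 | 0 | 100% | 92.9 to 100 |
| 50 | 1 | 98% | 89.4 to 99.9 |
| 50 | 2 | 96% | 86.3 to 99.5 |

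For k = 0 the lower bound is 0.025^(1/n): 0.025^(1/25) = 0.863 and 0.025^(1/50) = 0.929.

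**Step 3. Chance that it arises at all.** For an assumed rate r per limb and 25 independent limbs, P(at least one) = 1 − (1 − r)^25. This is 22% at r = 1%, 40% at 2%, 72% at 5% and 93% at 10%. The documents do not say which of these, if any, applies.

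**The case against.** A reader might infer that any limb with a short procedure is a full success on both primary endpoints and that the untreated GSV is never scored. The documents do not support that. Occlusion is anchored 3 cm below the SFJ, so residual proximal flow beyond that point fails the limb. The synopsis version of the reflux-free rate, read literally, would count residual reflux anywhere in the limb. VCSS and CEAP are assessed without any segment restriction, although they are secondary.

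There is also a reasonable case that the treated vein simply means the GSV. Section 8 places the procedure on the GSV, the follow-up scans assess the treated GSV, and Section 3 describes treating the whole vessel. On that reading the occlusion rate has no gap. The reflux sentence still refers to segments, however, and Section 10.3 shows that the protocol can contemplate a GSV treated in part.

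Incomplete procedures would not be invisible. Procedure details go on the Treatment Visit Case Report Form (CRF), malfunctions are reported to the sponsor, and re-interventions have their own form plus a deviation form. None of these is linked to a primary endpoint. The CRFs are not among the documents, so the length fields may already exist.

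Finally, scoring the treated segment is a legitimate measure of whether delivered energy closes the vein, and it may be the measure needed for comparison with the equivalent device, which is the stated hypothesis. That is a reason to keep the treated-segment rate. It does not justify leaving the scored length undefined.

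**Conclusion.** The point holds as a gap in the endpoint definition. Followed as written, the Section 5.1 reflux sentence lets a limb be reported reflux-free despite residual reflux in GSV that was meant to be treated. The synopsis conflicts with it, and no rule covers incomplete ablation. For occlusion the gap is conditional: it needs an untreated distal part and a reading of the treated vein as the length ablated.

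The size is 4 points per affected limb with 25 limbs and 2 points with 50. One limb lowers the exact 95% lower bound from 86.3% to 79.6%, or from 92.9% to 89.4%. These figures assume that all other limbs succeed and that the untreated part shows flow or reflux. If it does not, the rate does not change. The frequency of incomplete procedures is unknown, so the expected bias cannot be estimated, but in a study this small one limb visibly changes the headline rate.

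**What to change.** 1. Reconcile the synopsis with Section 5.1 so that the reflux-free rate has one definition, and define the treated vein and the treated segment.
2. Record on the Treatment Visit CRF the GSV segment planned for treatment from the baseline DUS, the length ablated, and the reason for any shortfall.
3. Report both primary rates over the planned segment, keeping the 3 cm SFJ exemption for occlusion. A limb fails when DUS shows flow (occlusion) or reflux (reflux-free rate) in any part of that segment. A shortfall alone, without observed flow or reflux, is not imputed as a failure.
4. Report the treated-segment rates alongside, for comparison with the equivalent device, together with the number of incomplete ablations.
5. Align Sections 10.1 and 10.2 so that the follow-up scan covers the planned segment.

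The cost is protocol wording and a few CRF fields. The baseline DUS and the follow-up scans of the treated limb are already scheduled, so no visit or scan session is added. The planned-segment rates may come out slightly lower than the treated-segment rates.

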5.2 SECONDARY ENDPOINTS

Secondary endpoints are the clinical outcomes (patient symptoms, patient recovery) and evaluation of side effects/adverse events after the treatment:

5.2.1 Patient Outcome (Symptoms/Recovery)

Clinical signs and symptoms of lower limb venous disease will be evaluated using standardized scales and subject responses to pre and post-procedure questions using the Clinical Etiologic Anatomic Pathophysiologic (CEAP) clinical classification and the 2010 revised Venous Clinical Severity Score (VCSS).⁴

Clinical Etiologic Anatomic Pathophysiologic (CEAP): Status of clinical signs and symptoms of lower limb venous disease as measured by CEAP Classification at baseline, and 3-day, and 3-, 6- and 12-month follow-up visits. CEAP clinical categories are as follows⁵:

C0: no visible or palpable signs of venous disease.

C1: telangiectasies or reticular veins.

C2: varicose veins.

C3: edema.

C4a: pigmentation or eczema.

C4b: lipodermatosclerosis or atrophie blanche.

C5: healed venous ulcer.

² Proebstle T, van den Bos R. Endovenous ablation of refluxing saphenous and perforating veins. *Vasa*. 2017 May;46(3):159-166. doi: 10.1024/0301-1526/a000610. Epub 2017 Feb 27. Review. PMID: 28238282

³ Creton D, Pichot O, Sessa C, Proebstle TM; ClosureFast Europe Group. Radiofrequency-powered segmental thermal obliteration carried out with the ClosureFast procedure: results at 1 year. *Ann Vasc Surg.* 2010 Apr;24(3):360-6. doi: 10.1016/j.avsg.2009.09.019. Epub 2010 Jan 29. PMID: 20116207

⁴ Vasquez et al., Revision of the venous clinical severity score: venous outcomes consensus statement: special communication of the American Venous Forum Ad Hoc Outcomes Working Group. *J Vasc Surg.* 2010 Nov;52(5):1387-1396.

⁵ Eklöf, B. et al, Revision of the CEAP classification for chronic venous disorders: Consensus statement, *Journal of Vascular Surgery*, Volume 40, Number 6, 1248-1252

Document Title: EU Post Market Clinical Follow-Up Study of the Venclose System for Saphenous Vein Incompetence

C6: active venous ulcer.

Venous Clinical Severity Score (VCSS): VCSS will be measured at baseline, 3-day, and 3-, 6- and 12-month follow-up visits. VCSS assesses 10 factors of venous disease for which each factor is graded on a severity scale of 0-3 (least to worst). The higher the VCSS score the most severe the clinical signs and symptoms of venous disease are in a patient. VCSS improvement over time is presented by a decrease in VCSS total score (maximum score = 30; minimum score = 0).⁶

Although ClosureFast studies utilized the original 1996 CEAP and 2000 VCSS scales, the Venclose post-market study will utilize the official 2004 and 2010 revised version of the scales, respectively, for consistency with the current state-of-the-art of clinical assessment for endovascular coagulation of blood vessels in patients with superficial vein reflux. Comparison efforts between the Venclose and ClosureFast studies will focus on similar percentages of score reduction, and may include an analysis of the differences in scale composition, as needed.

5.2.2 Side Effects and Complications

Side effects, adverse events and complications associated with the procedure will be recorded and analyzed. See Section 11.0 for Reporting of Adverse Events.

6 OVERVIEW OF STUDY DESIGN

Potential subjects presenting with signs and symptoms of chronic lower limb venous disease and significant reflux in the GSV will be further screened for study participation and enrollment. All enrolled subjects will meet study eligibility criteria as described in the inclusion and exclusion criteria sections below.

After voluntarily providing informed consent to participate, eligible subjects will undergo a minimally invasive procedure, which involves delivering controlled radiofrequency energy for ablation of the great saphenous vein (GSV). All procedures will be performed by surgeons determined to be experienced with the Venclose System and will take place at a single study site, Venenzentrum am Bruehl, [name]. The study will enroll up to 25 treated subjects. The study site will receive the Venclose System components for the treatment of study patients, free of charge.

After the treatment procedure, subjects will be evaluated four (4) times to determine the incidence of adverse events, and to assess vein recanalization and reflux. Follow-up visits occur at 3 days (+/-2 days), 3-months (+/- 2 weeks), 6 months (+/- 3 weeks) and 12 months (+/- 4 weeks) post-procedure. Each follow-up visit will consist of a clinical examination,

⁶ Vasquez et al., Revision of the venous clinical severity score: venous outcomes consensus statement: special communication of the American Venous Forum Ad Hoc Outcomes Working Group. *J Vasc Surg.* 2010 Nov;52(5):1387-1396.

Document Title: EU Post Market Clinical Follow-Up Study of the Venclose System for Saphenous Vein Incompetence

CIVIQ-20 Patient Questionnaire (except 3-day visit), patient satisfaction survey, and Duplex Ultrasound (DUS) examination of the treated limb in the reverse Trendelenburg position. A supine (rather than standing) position for DUS examinations is preferred in order to allow comparison with vein diameters obtained during the procedure.

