6.1 INCLUSION CRITERIA

- 1. Subject is male or female and 18 to 80 years old (inclusive) at time of enrollment (signing of consent).
- 2. Subject has significant venous reflux by DUS, defined as reverse flow with reflux duration greater than 0.5 seconds after the Valsalva maneuver or distal augmentation while the patient is standing or in reverse Trendelenburg position.
- 3. Subject is eligible for endovascular treatment, as determined by the treating investigator.
- 4. Subject's general physical condition allows for a significant amount of ambulation after the procedure, as determined by the treating investigator.
- 5. Subject is willing and able to complete study requirements, including all follow-up visits and assessments.
- 6. Subject voluntarily provides written informed consent to participate in this study.

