10 FOLLOW-UP STUDY VISITS

As shown in Table 1, Study Visit Schedule, all subjects will undergo four (4) follow-up examinations to assess the safety and efficacy of the treatment procedure. The visits will be scheduled at 3 days (+/-2 days), 3-months (+/- 2 weeks), 6 months (+/- 3 weeks), and 12 months (+/- 4 weeks) post-procedure. Each follow-up visit will consist of a clinical examination that includes DUS examination of the treated limb in the reverse Trendelenburg position, assessments using the Clinical Etiologic Anatomic Pathophysiologic (CEAP) Classification and the Venous Clinical Severity Score (VCSS), patient satisfaction survey, and CIVIQ-20 patient questionnaire (except 3-day visit). All follow-up data will be recorded on the *Follow-Up Visit Case Report Form*.

	Pre-surgical Assessment/ Baseline	Treatment Procedure	3 Days Post- Procedure (+/-2 days)	3 Months Post- Procedure (+/- 2 weeks)	6 Months Post- Procedure (+/- 3 weeks)	12 Months Post- Procedure (+/- 4 weeks)
Informed Consent	\checkmark					
Medical History and Physical Exam	\checkmark					
DUS	\checkmark		\checkmark	\checkmark	\checkmark	\checkmark
CEAP	\checkmark		\checkmark	\checkmark	\checkmark	\checkmark
VCSS	\checkmark		\checkmark	\checkmark	\checkmark	\checkmark
CIVIQ-20 Patient Question- naire	V			V	\checkmark	\checkmark

Table 1: Study Visit Schedule

Document Title: EU Post Market Clinical Follow-Up Study of the Venclose System for Saphenous Vein Incompetence

	Pre-surgical Assessment/ Baseline	Treatment Procedure	3 Days Post- Procedure (+/-2 days)	3 Months Post- Procedure (+/- 2 weeks)	6 Months Post- Procedure (+/- 3 weeks)	12 Months Post- Procedure (+/- 4 weeks)
Patient Satisfaction Survey			\checkmark	\checkmark	\checkmark	\checkmark
Treatment with Venclose System		\checkmark				
Medication Review	\checkmark		\checkmark		\checkmark	
Adverse Event Assessment		√**	1	1	1	\checkmark
Study Exit						\checkmark

** Adverse events will be assessed during the immediate post-procedure period, prior to discharge.

10.1 3-DAY FOLLOW-UP VISIT

During the 3-day post-procedure follow-up visit, the pads, gauze bandage and wrapping will be removed. The surgical wounds will be evaluated, and complications or adverse events recorded. Duplex ultrasound of the treated limb will be performed for an assessment of the deep venous system, including an assessment of the treated GSV for closure, patency or recanalization. A patient self-reported satisfaction survey will be administered.

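### Sections 6 and 10 omit the 15° tilt in the primary reflux definition, and Section 6 prefers supine scanning without a tilt, so a flat or under-tilted reflux test is not ruled out

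*Combined protocol and SAP*

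**What the plan says.** Four places in the protocol bear on posture.

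- **Section 5.1 (primary endpoints)** makes posture part of the endpoint: "Reflux is defined as reversal flow >0.5 seconds with subject standing or in reverse Trendelenburg position of at least 15° after distal augmentation".
- **Section 6 (overview of study design)** says each follow-up visit includes "Duplex Ultrasound (DUS) examination of the treated limb in the reverse Trendelenburg position". The sentence directly after it reads: "A supine (rather than standing) position for DUS examinations is preferred in order to allow comparison with vein diameters obtained during the procedure".
- **Section 10 (follow-up study visits)** repeats the first of these, "DUS examination of the treated limb in the reverse Trendelenburg position", and does not mention supine.
- **Section 6.1, inclusion criterion 2** tests reflux for entry "while the patient is standing or in reverse Trendelenburg position", after either a Valsalva manoeuvre or distal augmentation.

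Only Section 5.1 gives a minimum tilt. Sections 10.1 and 10.2 direct the DUS at the deep veins and at whether the treated vein is closed or has reopened; they mention neither reflux testing nor posture. Section 15 has no rule for scoring a scan made outside the defined posture.

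**The concern.** Section 5.1 scores reflux under a stated physical condition. A sonographer working from Sections 6 and 10 would not meet that condition in full. The tilt has no minimum there, and the supine preference names no tilt at all. The preference covers DUS examinations in general without exempting the reflux test, and its stated purpose is to compare vein diameters, which are not among the Section 5 endpoints.

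The limbs at risk are those with residual or recurrent flow, since a fully occluded vein has no flow to reverse in any posture. These are also the limbs that decide the rate. If such a limb is examined flat or barely tilted and no reversal is seen, it can be entered as reflux-free without the test that defines reflux having been done. The study exists to confirm performance, with a hypothesis of similarity to an equivalent device (Section 2). A reader of the results should be able to tell whether the endpoint was measured as defined.

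**Working it through.** The plan gives no figure to reproduce here, so the check is a comparison of the text followed by a scale calculation.

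**Passages side by side**

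| Place | Use | Posture | Minimum tilt |
|---|---|---|---|
| 5.1 | Scores the primary endpoint | Standing or reverse Trendelenburg | 15° |
| 6, first sentence | Conduct of follow-up DUS | Reverse Trendelenburg | None given |
| 6, next sentence | Preference for DUS | Supine over standing | Tilt not mentioned |
| 10 | Conduct of follow-up DUS | Reverse Trendelenburg | None given |
| 6.1 | Eligibility | Standing or reverse Trendelenburg | None given |

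**Which scans satisfy the conduct text but not Section 5.1?**

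1. Standing, or tilted by 15° or more: meets Section 5.1.
2. Reverse Trendelenburg below 15°: consistent with Sections 6 and 10, but fails Section 5.1.
3. Flat supine: at odds with the first sentence of Section 6 and with Section 10, but within the literal words of the Section 6 preference. It fails Section 5.1.

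So case 2 is permitted by the conduct text, and case 3 is not clearly ruled out by it.

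**Scale**

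- Input: "The study will enroll up to 25 treated subjects" (Section 6). The endpoint is a percentage of limbs (Section 5.1), and the note in Section 7.3 provides for bilateral treatment with limbs analysed separately.
- Assumption: full enrolment and all limbs scanned. The denominator n then runs from 25 (all unilateral) to 50 (all bilateral).
- Shift in the rate from k limbs wrongly scored reflux-free: k/n.
- k = 1, n = 25: 1/25 = 4.0 percentage points.
- k = 1, n = 50: 1/50 = 2.0 percentage points.

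Illustration, with the number of refluxing limbs assumed because the documents do not give it: if 2 of 25 limbs truly reflux, the rate is 23/25 = 92%. Missing one gives 24/25 = 96%; missing both gives 25/25 = 100%.

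**Effect of dropping doubtful limbs instead.** In the same illustration, removing the two limbs with flow as not evaluable gives 23/23 = 100%. That is the same figure as missing both, so exclusion does not remove the problem.

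**The case against.** The strongest reply is that Section 6 already sets the posture. The sentence before the supine preference calls for reverse Trendelenburg, and Section 10 repeats it for every follow-up visit. Reverse Trendelenburg is itself a lying posture on a tilted surface, and the parenthesis in the preference contrasts lying with standing, not flat with tilted. On that reading the plan simply chooses one of the two postures that Section 5.1 accepts. This is a fair reading and may be the intended one. A reader might infer that the protocol instructs flat scanning in conflict with its own endpoint; the documents do not support that. What survives is that the tilted reading still lacks the 15° minimum, and the flat reading is not excluded.

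Further points on that side:

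- **Follow-up steered away from standing.** This is not a defect in itself. Section 5.1 offers standing and sufficient tilt as alternatives and ranks neither.
- **The entry criterion.** Inclusion criterion 2 is an eligibility test with its own provocation options. Nothing in the documents shows that reflux found at a smaller tilt is invalid for entry, so adding 15° there would be a preference and not a correction.
- **Bias.** The documents do not explain why the posture was set and give no data on missed reflux. The direction is an inference from the fact that the definition demands an upright or tilted position; the size is unknown.
- **The other primary endpoint.** Occlusion fails a limb for any flow beyond the proximal 3 cm stump, with no posture or augmentation condition. A limb with detected flow but missed reflux would still be an occlusion failure. This protects the Vein Occlusion Rate, but not the Reflux-Free Rate, which is a separate primary endpoint.
- **No threshold.** Section 15 plans descriptive reporting and sets no reflux criterion that one limb could cross. This limits the consequence but does not settle whether the endpoint was measured as defined.

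**Conclusion.** The point holds as an inconsistency of measurement: an ambiguous preference in Section 6, and a 15° minimum in the endpoint definition that is missing from both sections describing follow-up conduct. It does not show that scans will be done flat or that the results will be biased by any stated amount.

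If a limb with residual flow is scanned in a non-qualifying posture, the likely error is towards reflux-free. Each such limb moves the rate by 4 points at 25 limbs or 2 points at 50, assuming full enrolment and complete scans; with fewer limbs than 25 the step is larger. The number of limbs affected cannot be estimated from the documents. Nor can it be told whether posture is already recorded, because the case report forms are not included. This is a cheap improvement, worth making because it concerns a primary endpoint.

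**What to change.** 1. In Sections 6 and 10, state that reflux is assessed at every follow-up visit, after distal augmentation, in a posture that meets Section 5.1: standing, or reverse Trendelenburg at 15° or more. Preferably use the same posture for a given limb across visits.
2. Limit the supine preference in Section 6 to vein-diameter measurement, separate from the reflux test.
3. Record posture and tilt angle on the Follow-Up Visit Case Report Form, if it does not already capture them.
4. In Section 15, add a rule for a limb with flow that was scanned in a non-qualifying posture:
   - Reflux seen counts as reflux.
   - If none is seen, repeat the test in a qualifying posture in the same session.
   - If that is not done, keep the limb in the denominator, do not count it as reflux-free, and show a sensitivity analysis with it counted as reflux-free. Do not drop it.

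The eligibility criterion can stay as it is.

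Cost: a few lines of protocol text, up to two form fields and slightly more scan time. The reported rate may be slightly less favourable.
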